3.3 Study Duration, Enrollment and Number of Subjects

The study is expected to be active for 1-2 years, while we enroll 95 subjects (45 in the placebo condition, 45 in the propranolol condition; with some potential for data loss).

Each subject's participation will last approximately seven hours over the course of approximately two weeks. They will complete a telephone screening for eligibility (~15-20 minutes), an in-person session finalizing eligibility, consent and completing a measure of interoceptive sensitivity (~30-60 minutes), and the intervention session, which will involve taking the study medication, blood draws, saliva samples, the psychological stress task, and computerized tasks and questionnaires (~5 hours). We expect approximately 1 week to pass between Session I and Session II.

3.4 Study Population

Participants in this study will be healthy, undergraduate students from the UNC- Chapel Hill community, between the ages of 18-25 who are fluent in English (spoken and written) and in good overall health.

Exclusion Criteria

- 1) presence or history of chronic physical illness (especially disorders with an inflammatory component, such as rheumatoid arthritis, asthma, allergies, or issues that can affect the heart, including low-blood pressure or other heart conditions)
- 2) presence or history of psychiatric illness (depression, anxiety)
- 3) any current prescription medication use
- 4) currently pregnant or planning to become pregnant;
- 5) engagement in a number of health-compromising behaviors that may affect levels of pro-inflammatory cytokines, including cigarette smoking, excessive caffeine intake and sleep disturbance (e.g., working night shifts);

- 6) body mass index (BMI) greater than 30, given that adiposity is known to relate to baseline levels of inflammation;
- 7) anxiety about or previous history of problems with blood draws (e.g., fainting)
- 8) any reported heart conditions

4 STUDY PROCEDURES (what will be done)

4.1 Screening Procedures and Baseline Visit

Prospective participants who email the Social Neuroscience and Health Lab regarding participation will first be screened via telephone by the lab manager or other trained research assistant in the lab to ensure they meet eligibility requirements. Eligible participants will then be scheduled for Session I. Participants who endorse one or more exclusionary criteria will be notified that they are not eligible for the present study, but will be encouraged to keep an eye out for flyers and announcements regarding other research projects in our lab if they are interested in participating in other studies. See attached telephone screening script for more information.

Session I will last approximately 30-60 minutes. Participants will enter the lab, meet the research assistant who is running the session, and read through the consent form. Once participants have been given a chance to ask any questions about the consent form and it is clear that they understand the protocol and are comfortable with proceeding, they will sign a copy of the General Consent Form. They will then follow the experimenter to a private testing room in our lab in Howell Hall, where our psychophysiological equipment for the heartbeat detection task is located (Howell 119). There, subjects are informed in greater detail about the procedure for the heartbeat detection task as a measure of their interoceptive or inner bodily awareness and also the conceptual knowledge questionnaires. Task descriptions, instructions, and an opportunity to ask questions will be provided to each participant. The heartbeat detection task will take about 20 minutes to complete, and will be administered by trained research assistants. Following completion of the heartbeat detection task, the experimenter will reiterate to the participant the general purpose of Session II and remind participants of their scheduled date for Session II. Participants are told that they do not have to complete Session II if they do not wish, and that they will still receive \$20 for Session I. Those participants who do *not* wish to continue the study will be paid and dismissed. Participants who ARE continuing with Session II will be reminded to get a good night's sleep before the next session, to not exercise or use over-the-counter medication the morning of the session, and to not intake any caffeine in the two hours before the beginning of the session. These instructions are given because sleep, exercise, anti-inflammatory use and caffeine intake are all known to impact levels of inflammation. Participants will also be asked to eat a satisfying meal and to be well-hydrated before coming to the lab for Session II, to lessen the likelihood of fainting during blood draws or fatigue during the session.

4.1 Intervention/Treatment procedures (by visits)

Session II (the intervention/treatment visit) will last approximately 5 hours and will take place in the emotion induction laboratory in Howell Hall at UNC-CH. When the participant arrives for the session, they will meet the lab manager and the nurse supplied by CTRC. The lab manager will give the participant a chance to review the consent form they signed during Session I, and will then remind the participant of the protocol and tasks in Session II. Once the participant understands the protocol and is comfortable with proceeding, the nurse will insert a catheter into the participant's non-dominant forearm, which will be used to draw all the blood samples. We use the catheter method so that participants do not have to be stuck with needles multiple times throughout the experiment. Once the catheter is placed, the participant will be given at least 45 minutes to acclimate to the catheter, during which time they will be prepared for psychophysiological data collection. We are collecting Heart Rate, Respiratory Sinus Arrhythmia, Cardiac Impedance, and Blood Pressure measures from participants throughout the session and, which will allow us to get a good index of participants' autonomic nervous system responses to the stress task, and will provide a biological "manipulation check" to ensure that the propranolol has had the intended effect (it should lower heart rate and blood pressure). Again, as with

Session 1, female research assistants will be assigned to female participants, while both male and female research assistants will be assigned to male participants, in an effort to reduce participant discomfort with the procedure of attaching the sensors. Once sensors have been attached, we will collect 5 minutes of baseline data while the participant just rests and relaxes.

Upon completion of the baseline psychophysiological measures, participants will complete trait questionnaire measures while they continue to acclimate to the catheter and the laboratory environment. Once 45 minutes has passed (around 1:15 PM), the nurse will draw the first (baseline) blood sample, and participants will be asked to provide the first (baseline) saliva sample. Next, the oral tablet of propranolol or placebo will be administered to the participant by the nurse. Participants will continue completing trait questionnaires and once finished, they will be given neutral reading material (magazines) to read while drug activation takes place. One hour after administration of the medication (or placebo), the nurse will draw a second blood sample, and participants will be asked to provide a second saliva sample. We will also collect another 5 minutes of psychophysiological data.

Next, the Trier Social Stress Task (TSST; Kirschbaum, Pirke, & Hellhammer) procedures will be explained to participants. The TSST is a commonly-used acute stress test to measure psychological and biological responses to stress in the laboratory. In this task, participants will be asked to prepare for and give a 10-minute speech and complete a difficult mental arithmetic task as they are evaluated by trained interviewers. The nature of the task is stressful and participants may experience varying levels of stress, anxiety, and possibly embarrassment. The consent form at the beginning of the study describes that they will take part in a “role play” during a cognitive performance task (see Consent Form). We describe the task in this vague way in the initial consent because we want to ensure that the baseline physiology data is clean and not impacted by participants' anticipatory stress about the upcoming task. Additionally, prior to the participant's participation in the TSST, participants will be informed in greater detail about the procedure for TSST, and they will be asked if they would like to continue. If they do continue, but wish to stop at any time, they will be reminded that they can.

After being informed of the procedures and confirming participants would like to continue, the experimenter will introduce two more researchers who will act as the interviewers / judges. Participants will have 2 minutes to prepare for the speech, in which they will be asked to answer why they are the perfect candidate for their dream job. Participants will then give a 10 minute speech in front of the two interviewers and a video camera. After the 10 minute speech, participants will complete a verbal math task for 5 minutes. While participants are completing the tasks, interviewers will remain neutral (give neither positive nor negative feedback). The experimenter leading Session II will also be present throughout, to help with timing the tasks, etc.

Following completion of the TSST procedures, participants will complete a second round of questionnaires to measure their affective responses, somatic responses, and interpersonal appraisals during and after the TSST. Fifteen minutes after termination of the TSST, a third saliva sample will be taken, and 30 minutes after the termination of the TSST, a fourth (and final) saliva sample, and third blood sample, will be taken. Additional blood samples will be taken 60 minutes (sample #4) and 90 minutes (sample #5) following termination of the TSST. In between blood samplings, participants will be given neutral reading material. Following collection of the final blood sample, the nurse will remove the catheter and check the participant's vital signs. The nurse will then be dismissed back to the CTRC.

For the remaining 60 minutes of the session, participants will complete four computerized tasks designed to measure other psychological processes (besides stress) thought to be influenced by sympathetic nervous system activation. A list of tasks and questionnaires is included below.

In addition, at the completion of the study, participants will be fully debriefed. Contact information for the PI, Study Physician, and IRB is provided on the consent form and debriefing form (which participants can keep) if they wish to address any concerns they had.

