6.2 Secondary Endpoints- Statistical Methods

Analysis Plan. To address secondary objectives, we will follow the identical procedure outlined above, but will swap in the relevant outcome as the dependent variable (i.e., cortisol, salivary alpha amylase, PEP, RSA, psychological responses). We will first examine if there was a change in the outcome simply as an effect of taking the propranolol (before stress induction). As such, we will conduct a multilevel model (MLM) examining levels of the outcome, with time (BL vs. pre-TSST) as a within-subjects factor and condition (propranolol vs. placebo) as a between-subjects factor. If the result of this test shows a significant interaction, then we will only include the pre-TSST time point in subsequent models. If non-significant, we will use both baseline time points in subsequent analyses. Next, we will conduct an MLM examining levels

of each relevant outcome, with time (BL and/or pre-TSST, post-TSST time-points) as a within-subjects factor and condition (propranolol vs. placebo) as a between-subjects factor.

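### The resting cardiac baseline is recorded before catheter acclimation ends, while the blood and saliva baselines wait for it: an avoidable source of noise in PEP and RSA, but not a bias in the drug contrast

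*Combined protocol and SAP*

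**What the plan says.** Section 4.1 (Intervention/Treatment procedures) sets out the order of Session II. After catheter insertion, "the participant will be given at least 45 minutes to acclimate to the catheter, during which time they will be prepared for psychophysiological data collection". The autonomic baseline follows sensor attachment directly: "Once sensors have been attached, we will collect 5 minutes of baseline data while the participant just rests and relaxes". Afterwards, "participants will complete trait questionnaire measures while they continue to acclimate to the catheter and the laboratory environment", so the plan itself treats acclimation as unfinished when the recording ends. The biological samples come later: "Once 45 minutes has passed (around 1:15 PM), the nurse will draw the first (baseline) blood sample", together with the first saliva sample. Dosing is the next step: "Next, the oral tablet of propranolol or placebo will be administered to the participant by the nurse". About an hour after dosing, at the second blood and saliva samples, "We will also collect another 5 minutes of psychophysiological data".

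Section 6.2 applies the primary-endpoint procedure to PEP and RSA. Step 1 compares BL with pre-TSST by condition, to detect change due to the drug alone. If the interaction is significant, BL is dropped and only pre-TSST goes forward. Otherwise, "If non-significant, we will use both baseline time points in subsequent analyses". Section 4.1 also names heart rate and blood pressure as the biological check that propranolol has worked, and expects both to be lower.

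**The concern.** The plan sets a minimum acclimation time and holds the blood and saliva baselines until it has passed. It does not hold the cardiac baseline to the same rule, although that recording follows a needle insertion and sensor placement more closely than any other measurement. No number of minutes after insertion is fixed for it, so the interval may differ between participants.

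If heart rate, blood pressure, PEP or RSA are still settling during the recording, the change from BL to pre-TSST contains settling as well as any drug effect. At stake are the precision of the step 1 test for two secondary outcomes, the reading of the manipulation check, and whether BL means the same moment for every outcome.

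**Working it through.** **Timeline from Section 4.1.** Time 0 is catheter insertion.
- Acclimation ends at 45 minutes or later, around 1:15 PM. Insertion is therefore at about 12:30 PM (1:15 PM minus 45 minutes).
- The cardiac baseline lasts 5 minutes, comes after sensor attachment, and ends before acclimation does. Its latest start is 45 − 5 = 40 minutes. Its earliest start depends on sensor time, which is not given.
- Baseline blood and saliva come at 45 minutes or later, and the tablet follows.
- The pre-TSST recording comes at about 45 + 60 = 105 minutes or later.

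For IL-6, cortisol and alpha amylase, BL to pre-TSST spans about 60 minutes. For PEP and RSA it spans about 60 minutes plus whatever was left of the acclimation period.

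**Does a shared shift bias the drug contrast?** Suppose BL lies d above the settled level in both arms, which is what randomization gives in expectation because BL is pre-dose.
- Step 1: each arm's change from BL is moved by −d. The difference between arms is (change in propranolol − d) − (change in placebo − d), and d cancels.
- Stress model with BL kept: suppose, for illustration, that BL and pre-TSST are weighted equally. The responses become Rp − d/2 (placebo) and Rd − d/2 (propranolol), where Rp and Rd are the true responses. Their difference is Rp − Rd, unchanged.
- Simulation of step 1 as a t-test on change scores (45 per arm, two-sided alpha 0.05, 20,000 runs, total SD 1, within-person correlation 0.7, shared shift of 0, 0.25 or 0.5 SD): the estimated interaction was 0.00 when the true effect was 0, and 0.50 when it was 0.5. Type I error was 4.8% to 5.2%, a range that includes the case where settling also varies between people.

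**What a shared shift does distort.** In the same simulation, with no true change, the placebo arm's mean change from BL was −0.25 SD for a shift of 0.25 and −0.50 SD for a shift of 0.5. Within-arm change from BL is therefore confounded with settling.

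**Settling that varies between people.** The 45 per arm comes from Section 6.4 and the alpha of 0.05 from Section 6. Assumed, because the documents give no values: total SD 1, within-person correlation 0.7, drug effect 0.5 SD, settling SD s.
- Variance of the change score = 2(1 − 0.7) + s² = 0.6 + s².
- SE of the difference between arms = √[(0.6 + s²) × 2/45].
- Power ≈ Φ(0.5/SE − 1.96).

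| s | Variance | SE | 0.5/SE | Power |
|---|---|---|---|---|
| 0 | 0.60 | 0.163 | 3.06 | about 86% |
| 0.25 | 0.6625 | 0.172 | 2.91 | about 83% |
| 0.5 | 0.85 | 0.194 | 2.57 | about 73% |

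The simulation gave 86.1% for s = 0 and 72.5% for s = 0.5, in agreement with the formula. Lower power in step 1 also makes a non-significant result more likely, and that is the result that keeps BL in the stress model.

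**The case against.** The strongest reply is that the comparison that matters is protected. BL is pre-dose in both arms, so shared settling cancels. A reader might infer that an aroused baseline shrinks the placebo stress response and so leaves less for propranolol to attenuate. The algebra does not support that: the same amount is removed from both arms and the difference is unchanged. Nor does Section 6.2 say that BL and pre-TSST are averaged into one reference. With time as a categorical factor, the pre- to post-TSST change is available without BL.

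A reader might also infer that the recording is known to be unsettled. The documents give neither the minutes from insertion nor a settling time for PEP or RSA, and the participant is resting during the recording. Nor is BL the only reference. A second recording precedes the stressor, and BL is dropped when step 1 is significant. That is plausible for PEP, because the plan expects cardiac effects of the drug. All of this stands, and it limits the point to precision, within-arm interpretation and comparability.

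Two further replies carry less weight. The plan says "We are collecting Heart Rate, Respiratory Sinus Arrhythmia, Cardiac Impedance, and Blood Pressure measures from participants throughout the session", so a later pre-dose stretch may exist. However, no other pre-dose resting epoch is described, and participants are completing questionnaires in that interval. It can also be argued that recording before questionnaires protects the cardiac baseline from items on anxiety or speech-giving. That trade-off is real but manageable: the blood and saliva baselines and the pre-TSST recording already follow questionnaires, and Section 4.1 lets questionnaires continue after dosing.

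**Conclusion.** The point holds as a minor design weakness. The order of steps is plain from Section 4.1, and the use of BL is plain from Section 6.2. The documents do not support a claim of bias in the propranolol-placebo contrast, nor any effect on the primary IL-6 endpoint, whose baseline is drawn after acclimation.

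Three things remain:
- avoidable noise in the step 1 contrast for PEP and RSA if settling differs between people;
- falls in heart rate or blood pressure from BL within the propranolol arm that cannot be attributed to the drug, because settling may act in the same direction;
- a BL that is a different moment for PEP and RSA than for IL-6 and cortisol.

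The true size is unknown. The fall in power from about 86% to 73% is only an illustration. It rests on the assumed correlation of 0.7, settling SD of 0.5 and drug effect of 0.5 SD, and it applies to step 1 alone. At a settling SD of 0.25 the figure is about 83%.

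**What to change.** In Section 4.1 and the session flow sheets, keep sensor attachment where it is and have participants complete trait questionnaires during acclimation. Record the 5-minute resting baseline once the 45 minutes are up, immediately before the baseline blood and saliva samples and the tablet. BL then refers to the same moment for all of these outcomes. In the analysis plan, state that the heart-rate and blood-pressure manipulation check is judged by the comparison between arms, not by within-arm change from BL.

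The cost is small: an existing recording moves, and no procedure, staff or equipment is added. The one downside is that some questionnaires would precede the cardiac baseline. Those on anxiety, fear of evaluation and comfort with speeches can be placed in the questionnaire period after dosing that Section 4.1 already provides.

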1.3 Non-Clinical and Clinical Study Findings

Propranolol blocks the effects of epinephrine and norepinephrine by competitively binding to both β_1 - and β_2 -adrenergic receptors in both the peripheral and central nervous system. It was originally used to treat hypertension, approved by the FDA in 1965. Since then it has been FDA-approved for a variety of other indications, including migraine prevention, and essential tremor. It is even approved for certain pediatric conditions. Propranolol is one of the historically most commonly-used prescription medications, and it is generally viewed as a safe, nontoxic medication in the daily dosage range of up to 640 mg, divided into 2-4 doses per day. The 40mg dose to be given here is expected to be well-tolerated, with the most adverse side effect anticipated being the possibility of allergic reaction. Propranolol rarely causes side effects, including: hypotension, insomnia, fatigue, light-headedness, nausea, bronchospasm, dizziness, headache, hyperglycemia, and muscle weakness. Each of these side effects is uncommon at the low, single dosage being utilized in these studies. Moreover, these side effects are not only rare, but also quite mild and rarely prolonged (i.e. < 1-2 hours) when they do occur. If any of these side effects do occur, the subjects will be given a comfortable place to lie down until the symptoms pass, and will be monitored by the CTRC nurse and the project coordinator.

Studies of the pharmacokinetics of propranolol suggest that peak plasma concentrations following a 40 mg dose occur 1-2 hours after administration; as such, we will have participants rest quietly for 1 hour following administration of the medication before the start the stress task. Plasma half-life of propranolol is 3-6 hours, and as such, we will examine our more exploratory aims at the end of the session, which is still within the half-life of the drug.

The study MD will be on-call during all intervention sessions to assess any side effects and prescribe appropriate management as needed, and a CTRC nurse will be present throughout the majority of study procedures. Given that we do not anticipate any serious side effects to occur and that there is currently no data

to suggest that an acute dose of propranolol leads to serious side effects in healthy populations, we believe the facilities at Howell Hall are sufficient to manage the mild, transient side effects that may occur in response to taking propranolol.

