Saliva Samples. We will take 4 saliva samples during the study via the passive drool method. Passive drool is a saliva collection method for collecting whole saliva. Passive drool is considered by many researchers to be the gold standard when collecting saliva samples for biological testing, because it provides the purest sample possible and allows researchers to "biobank" samples for testing. Participants allow saliva to pool in mouth, then, with head tilted forward, gently force saliva through a small straw and into the vial. Participants will be aided by trained research assistants wearing rubber gloves. About 2ml of saliva will be collected at each sampling time. Saliva samples will be assayed for levels of the stress hormone, cortisol, as well as another HPA axis byproducts including ACTH and testosterone.

Blood Samples. We will draw 10 mL of blood into vacutainer EDTA tubes at each time point, which will be stored on ice for the duration of the study, and then centrifuged to isolate plasma and stored in 1 mL aliquots in cryovials in a -80 degree freezer until the study is complete. Samples will then be assayed for levels of pro-inflammatory cytokines (i.e., interleukin-6, tumor necrosis factor alpha, interleukin-1) using multiplex bead-based assays.

Psychophysiology. We will collect electrocardiogram and impedance cardiography data from participants to examine how propranolol and exposure to the TSST influence autonomic physiology.

Questionnaires (for exploratory moderator analyese):

Demographics.

We ask participants' age, gender, race/ethnicity, weight/height (to calculate BMI), perceived SES, and also about participants' comfort with giving speeches / being the center of attention.

Health Behavioral Questionnaire ([name], 2016). This asks a series of questions to make sure that participants followed instructions prior to the session and are still eligible to participate. It includes items "Which medications have you taken in the last 48 hours?"

UCLA Loneliness Scale: (Russell, D., Peplau, L.A., and Ferguson, M.L 1978) This is a commonly used, 10 item, measure of loneliness.

The PHQ-9: (Spitzer, 1999) This a multipurpose, validated instrument for screening, diagnosing, monitoring and measuring the severity of depression.

Perceived Stress Scale: (Cohen, 1994) This is a widely used psychological instrument for measuring the perception of stress; i.e the degree to which situations in one's life are appraised as stressful.

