Social Provisions Scale (Cutrona, C. E. and Russell, D., 1987). This examines the degree to which respondent's social relationships provide various dimensions of social support.

Fear of Evaluation Scale (Leary 1983). This is a 30-item, self-rated scale used to measure social anxiety.

State-Trait Anxiety Inventory (Spielberger 1983) this inventory has 40 self-report items pertaining to anxiety affect.

The MacArthur Scale of Subjective Social Status: (Adler, 1984) This is a commonly used measure subjective social status. In an easy pictorial format, it presents a "social ladder" and asks individuals to place an "X" on the rung on which they feel they stand. There are two versions of the ladder, one linked to traditional SES indicators and the second linked to standing in one's community, in this case UNC. We will give them both. It is useful to be able to make comparisons between objective and subjective SES.

Parent SES: This is a six item questionnaire to assess the socioeconomic status of the participant and their family. It will be used to make comparisons between objective and subjective SES.

PANAS-circumplex questionnaire. Participants rate which emotions they felt during the TSST and also how they are feeling currently. Participants rate how intensely they felt those emotions using a Likert

scale. Additionally, participants report how clear their emotions were during the TSST. This is our measure of discrete emotion, perceived emotional intensity, and perceived emotional clarity.

Somatic Sensations questionnaire. Participants rate which somatic sensations they felt during the TSST and also rate how clearly / distinctly they experienced those bodily changes. Participants use Likert scales for their ratings. We will also assess the participants' feelings about the interviewers using standardized measures.

Challenge threat appraisals: Blascovich, J. & Mendes, W. B. (2000). This questionnaire taps into the degree to which the participant views new experiences as a potential challenge or threat.

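### Trait questionnaires may continue after the tablet, so some scores intended as exploratory moderators may be collected after treatment (minor; cheap to prevent)

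*Combined protocol and SAP*

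**What the plan says.** Section 4.1 (Intervention/Treatment procedures) gives the Session II sequence. After catheter placement, "the participant will be given at least 45 minutes to acclimate to the catheter". Sensor preparation and a 5-minute resting recording fall within that time, and then "participants will complete trait questionnaire measures while they continue to acclimate to the catheter and the laboratory environment". At around 1:15 PM the baseline blood and saliva samples are taken and the tablet is given. The text continues: "Participants will continue completing trait questionnaires and once finished, they will be given neutral reading material (magazines) to read while drug activation takes place". The second blood sample follows one hour after the tablet.

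Section 5 lists the instruments under a single heading, "Questionnaires (for exploratory moderator analyese)". The list includes the PHQ-9, the Perceived Stress Scale and the State-Trait Anxiety Inventory, of which it says "this inventory has 40 self-report items pertaining to anxiety affect". It also includes ratings of the stress task, which section 4.1 places after that task: "participants will complete a second round of questionnaires to measure their affective responses, somatic responses, and interpersonal appraisals during and after the TSST". No section says which instruments make up the trait round or in what order they are given.

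Three other sections bear on this. Section 6.4 gives interest in moderators as the reason for enrolling more participants than prior studies. Section 10 says that flow sheets specify when questionnaires take place and that administration times are recorded. Section 6 sets out no moderator model and no rule limiting moderators to scores obtained before dosing.

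**The concern.** A moderator of a drug effect should be fixed before the drug is given. If the drug alters the recorded score, the score differs in meaning between arms, and an arm-by-score interaction can appear or disappear for reasons unrelated to true moderation. Here, completion after dosing is part of the written procedure and not a deviation from it. The exposed window is the hour after the tablet. Section 1.3 says "peak plasma concentrations following a 40 mg dose occur 1-2 hours after administration", so the drug is being absorbed while any remaining scales are filled in.

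Stable traits and factual items (demographics, height and weight, family socioeconomic status) are unlikely to move in an hour. A scale that asks how the person feels now could. A score completed after dosing cannot be collected again as a pre-dose score.

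**Working it through.** The plan states no figure on this point, so there is none to reproduce. The documents also give neither the share of participants who finish late nor any drug effect on scores. Those inputs below are assumptions, shown as ranges.

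**1. Is there room before the tablet?** Acclimation is at least 45 minutes. Less the 5-minute recording and an assumed 10-20 minutes of sensor preparation, 20-30 minutes remain. Scales with a stated count have 10 (loneliness) + 30 (fear of evaluation) + 40 (State-Trait Anxiety Inventory) + 6 (parent SES) = 86 items. At an assumed 5-10 seconds per item:
- 86 items take 7.2-14.3 minutes.
- The 40-item inventory alone takes 3.3-6.7 minutes.

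Scales without a stated count come on top.

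**2. Effect on an interaction test.** Take 45 per arm (section 6.4), outcome Y = b·M + error, and a true interaction of zero. In the drug arm a random share f has the recorded score M' = M(1 − c) − d, where c is compression and d a uniform fall in SD units; all others have M' = M. The test is arm-by-score, two-sided 5%, 86 df, with 40,000 simulated trials per cell. The false slope is

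b·[(1 − cf)/(1 − 2cf + c²f + d²f(1 − f)) − 1].

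*Uniform fall* (c = 0, d = 0.2 or 0.5, f = 0.25-1): the largest false slope is at b = 0.5, d = 0.5, f = 0.5, namely 0.5·[1/(1 + 0.25·0.25) − 1] = −0.029. Rejection is 4.7%-5.2%, which is near nominal.

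*Compression* (c = 0.1-0.4; d = 0 or d = c; residual SD 1 or total SD 1):

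| Share late (f) | False slope (b = 0.5, c = 0.4, d = 0) | Rejection, b = 0.3 | Rejection, b = 0.5 |
|---|---|---|---|
| 25% | 0.5·(0.90/0.84 − 1) = 0.036 | 4.9%-5.2% | 4.9%-5.4% |
| 50% | 0.5·(0.80/0.68 − 1) = 0.088 | 4.9%-5.7% | 4.9%-7.4% |
| 75% | 0.5·(0.70/0.52 − 1) = 0.173 | 4.9%-7.3% | 5.3%-12.3% |
| All | 0.5·(0.60/0.36 − 1) = 0.333 | 5.2%-10.8% | 5.5%-25.2% |

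**3. A second route.** The drug effect on the score need not depend on the baseline score. If it varies between people with an assumed SD of 0.5, unrelated to M, and everyone answers late, the variance of the recorded score rises from 1 to 1 + 0.25 = 1.25. The false slope is then 0.5·(1/1.25 − 1) = −0.10, between the 50% and 75% rows above in size. The table is therefore not an upper limit.

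**4. Could comparing scores between arms clear them afterwards?** Power ≈ Φ(d·√(45/2) − 1.96): 16% at 0.2 SD, 30% at 0.3, 48% at 0.4 and 66% at 0.5. The difference detectable with 80% power is (1.96 + 0.84)·√(2/45) = 0.59 SD. A non-significant comparison would not show that the scores were untouched.

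**The case against.** The strongest case against is that this is a request for clarification about an exploratory analysis. Five parts of it deserve an answer.

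- *Flow sheets.* They specify questionnaire timing and may already put the sensitive scales first. A reader might infer that the order is uncontrolled; the documents show only that it is not stated in the text. Even so, section 4.1 expressly permits completion after the tablet.
- *Which scales.* A reader might infer that the State-Trait Anxiety Inventory is answered after dosing. The documents do not place it in the trait round, or say when its items are given. It is an example of where the concern would be greatest, not an established case.
- *Trait stability and time.* Measures labelled trait are meant to be stable, and the counted items may well fit before the tablet. This makes a large late share less likely, but it does not exclude one, because several scales have no stated length.
- *No shown drug effect.* Nothing in the documents shows that the drug changes these scores at rest in the first hour. This stands, and it is why the size of any bias is unknown.
- *Randomized, blinded, exploratory.* Blinding does not prevent a pharmacological effect on a score. The exploratory label limits the consequences but is no reason to accept an avoidable ambiguity, given that section 6.4 uses moderators to justify the sample size.

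**Conclusion.** Minor, but it holds. The written procedure allows some moderator scores to be collected after treatment, and no rule keeps those scores out of the moderator analyses. With 25%-50% of the drug arm late and scores compressed by 10%-40%, the assumed model gives rejection of about 4.9%-7.4% at a nominal 5%. A uniform shift leaves it near 5%. Larger figures need most participants to answer late and a strong, uneven drug effect.

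Two stronger readings are not supported. The 25.2% figure is not a forecast: it needs 40% compression, a slope of 0.5 and every drug-arm participant late, and nothing in the documents supports that combination. Nor does the point reach the primary IL-6 test or the secondary tests. The trait scores do not enter those models, and the covariates that section 6.1 may add (sex, BMI, objective SES) are not things the tablet can change. Conversely, the ranges are not a guarantee of harmlessness, because variation in drug response between people can distort the interaction as well.

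**What to change.** In section 4.1, and on the flow sheets, add: *Questionnaires to be used as moderators will be completed before the tablet, in the Session II acclimation period, state-sensitive scales first; any questionnaire continued after the tablet will not be used as a moderator in the main moderator analysis.*

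For participants already run, where the recorded times show that a scale was completed before dosing, repeat the moderator model on those scores as a sensitivity analysis. Section 10 promises administration times, not a completion time for each scale, so this may not be possible for every score. Completion before dosing is settled before the tablet, so the restriction does not depend on arm, although it may select faster respondents. It also costs precision: the interaction SE widens by √(45/34) = 1.15, or 15%, if 34 of 45 per arm remain, and by √(45/22) = 1.43, or 43%, if 22 remain.

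No participants or visits are added. Acclimation may run slightly longer and push the baseline draw past about 1:15 PM, or a few scales that do not fit are lost as moderators. Stable scales could go to Session I instead, but that lengthens a 30-60 minute session, and they would have to be kept apart from its counterbalanced tasks. They would also be measured earlier: "We expect approximately 1 week to pass between Session I and Session II".
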